9.2.1 Hematology

The following laboratory tests will be included: complete blood count (CBC).

9.2.2 Chemistry

The following laboratory tests will be included: blood urea nitrogen (BUN), blood sugar, electrolytes (sodium, chloride, and bicarbonate [HCO₃]), alkaline phosphatase, AST, ALT, lactate dehydrogenase (LDH), total bilirubin, serum creatinine, C-reactive protein, and fecal calprotectin.

9.3 Vital Signs

Vital signs will be measured on Days 1, 4, 8, 15, 22, 29, 36, and 43. Vital signs include systolic and diastolic blood pressure (mmHg), pulse rate (beats/min), blood oxygen saturation SpO₂, and temperature (°C) with method of measurement (axillary, oral, rectal, or tympanic).

Summary tables displaying observed values and changes from baseline will be presented for numeric vital sign data by treatment group for subjects in the Safety set. Changes from baseline to each scheduled post-baseline visit (Days 4, 8, 15, 22, 29, 36, and 43) will be presented.

All vital sign data will also be presented in a listing.

10. Exploratory Analysis

Exploratory analyses will be conducted on exploratory data collected at the Month 4 and Month 6 visits during the long term follow-up and will be included as the End of Study Final Analysis in an addendum to the main CSR.

All exploratory analyses will be performed using the FAS and will be presented separately for Part 1 and Part 2 of the study unless otherwise specified. Due the exploratory nature of these analyses, only descriptive summary statistics will be provided by treatment group and no inferential statistical tests will be performed.

All exploratory data including deaths will also be presented in separate listings.

10.1. Proportion of subjects with recurrence of COVID-19 symptoms during long term follow-up

A summary table will include the number and percentage (proportion) of subjects with any recurrent COVID-19 symptoms during the entire long term follow-up, after Day 43 visit to Month 4 visit and after Month 4 visit to Month 6 visit by treatment group. Only subjects who continued into the long term follow-up will be included in the summary and counted as the denominator for proportion. Additionally, the summary table will also include the number and percentage of subjects reporting each individual recurrent COVID-19 symptom by treatment group.

10.2. Proportion of subjects with persistence of COVID-19 symptoms during long term follow-up

A summary table will include the number and percentage (proportion) of subjects with any persistent COVID-19 symptoms during the entire long term follow-up, beyond Day 43 visit to Month 4 visit and beyond Month 4 visit to Month 6 visit by treatment group. Only subjects who continued into the long term follow-up will be included in the summary and counted as the denominator for proportion. Additionally, the summary table will also include the number and percentage of subjects reporting each individual persistent COVID-19 symptom by treatment group.

10.3. Proportion of subjects with new hospitalization or rehospitalization during long-term follow-up

A summary table will include the number and percentage (proportion) of subjects with any new hospitalization or rehospitalization during the entire long term follow-up, after Day 43 visit to Month 4 visit and after Month 4 visit to Month 6 visit by treatment group. Only subjects who

continued into the long term follow-up will be included in the summary and counted as the denominator for proportion. A subject will be considered as having a new hospitalization or rehospitalization if the subject has at least one hospitalization with an admission date after the Day 43 follow-up visit. Hospital admissions and dates of stay are collected on the Hospitalizations eCRF.

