Safety and tolerability secondary endpoints are: (n) all-cause mortality 6 weeks after randomization; (o) proportion of patients with treatment-emergent adverse events (TEAEs) leading to study drug discontinuation; (p) serious adverse events (SAEs); (q) clinically significant changes in laboratory measurements; and (r) clinically significant changes in vital sign measurements.

The **exploratory endpoints** will all compare the niclosamide arm to the placebo arm. These exploratory endpoints will be assessed for both Part 1 and Part 2:

(r) all-cause mortality 4 months and 6 months after randomization; (s) proportion of patients with recurrence of COVID-19 symptoms after Day 43, at 4 months and 6 months after randomization; (t) proportion of patients with persistence of COVID-19 symptoms beyond Day 43, at 4 months and 6 months after randomization (u) proportion of patients with new hospitalization or rehospitalization after Day 43, at 4 months and 6 months after randomization; and (v) summarization of genotypic resistance analysis data.

Statistical Methods

Statistical methods will be further detailed in the statistical analysis plan (SAP).

Sample size:

Part 1: The sample size was selected empirically for an initial evaluation of safety in patients with

COVID-19

Part 2: The sample size was determined by simulations based on the following assumptions:

- The time to fecal viral clearance has an exponential distribution for each treatment arm.
- The median time to fecal viral clearance is anticipated to be approximately 21 days for placebo arm and 10 days for niclosamide arm.
- Fecal viral clearance assessments are performed at Day 3, 7, 14, 28, 42 after first dose.
- Log-rank test (2-sided) is conducted to compare treatment difference.

Using a 1:1 randomization ratio, a sample size of 30 patients per treatment arm (60 patients total with a positive stool test for SARS-CoV-2 on Day 1) provides 74% power to detect a significant treatment difference for $\alpha=0.05$ and 83% power for $\alpha=0.10$. It is expected that approximately 40% of COVID-19 patients will be positive for SARS-CoV-2 in the stool sample. Therefore, approximately 150 patients with COVID-19 are needed to be enrolled/ randomized to ensure 60 patients have a positive stool test for SARS-CoV-2 on Day 1.

Analysis:

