8.3 Exploratory Endpoints

The exploratory endpoints will all compare the niclosamide arm to the placebo arm. These exploratory endpoints will be assessed for both Part 1 and Part 2:

- a. All-cause mortality 4 months and 6 months after randomization.
- b. Proportion of patients with recurrence of COVID-19 symptoms after Day 43, at 4 months and 6 months after randomization.
- c. Proportion of patients with persistence of COVID-19 symptoms beyond Day 43, at 4 months and 6 months after randomization.
- d. Proportion of patients with new hospitalization or rehospitalization after Day 43, at 4 months and 6 months after randomization.
- e. Summarization of genotypic resistance analysis data.

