10.6 Four and Six Months After First Dose (± 1 week): Long-Term Follow-Up

The patient will be contacted 4 months and 6 months after the first dose of study drug (± 1 week) to collect:

- Survival status
- Persistence of COVID-19 symptoms beyond Day 43
- Recurrence of COVID-19 symptoms after Day 43
- Hospitalization or rehospitalization due to COVID-19 after Day 43

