16.1 Appendix A - Schedule of Assessments

Visit ¹	Screening ²	Treatment				Follow-up					
						Short-term				Long-term	
Timing (D=day, M=month)	D -3 to -1	D1	D4	D8	D15	D22	D29	D36	D43	M4	M6
Deviation vs randomization day			±1 day	±1 day	±2 days	±2 days	±2 days	±3 days	±3 days	±1 week	±1 week
Informed consent	X										
Eligibility (inclusion/exclusion criteria)	X	X									
Demography	X										
Medical history (or changes)	X	X	X	X	X	X	X	X	X		
Pregnancy test (urine or serum)	X				X						
Stool analysis	X										
Stool sample for SARS-CoV-2 RNA ³	X	X	X	X	X	X	X	X	X		
Diarrhea clinical assessment	X	X	X	X	X	X	X	X	X		
Nasopharyngeal swab for SARS-CoV-2 RNA ³	X	X	X	X	X	X	X	X	X		
Laboratory assessments ⁴ (L=local, C=central)	L	C		C	C		C		C		
Overall clinical assessment ⁵	X	X	X	X	X	X	X	X	X		
Randomization		X									
Dosing study drug		Daily TID, with last dose on D14 or 15									
Daily diary		Daily									
Adverse events	X	X	X	X	X	X	X	X	X		
Concomitant medications		X	X	X	X	X	X	X	X		
Survival status										X	X
Persistence of COVID-19 symptoms										X	X
Recurrence of COVID-19 symptoms										X	X
(Re)Hospitalization due to COVID-19										X	X

- ¹ Patients may be hospitalized, inpatient in a research unit, or seen in an outpatient clinic or in a home care setting.
 - ² Screening may occur on the same day as randomization, if all procedures may be completed. If they occur on the same day, procedures scheduled for both visits are not required to be duplicated.
 - ³ At screening, eligibility can be determined by local SARS-CoV-2 viral RNA analysis on a nasopharyngeal swab. Only one screening sample is required and can be determined by local requirements. Eligibility can be determined at a local laboratory at screening; however, a central laboratory may be used at screening if needed. On Days 1 to 43, the nasopharyngeal swab and stool sample will be collected and sent to the central lab.

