3.2.3. Exploratory Endpoints

- s) All-cause mortality 4 months and 6 months after randomization.
- t) Proportion of subjects with recurrence of COVID-19 symptoms after Day 43 at 4 months and 6 months after randomization.
- u) Proportion of subjects with persistence of COVID-19 symptoms beyond Day 43 at 4 months and 6 months after randomization.
- v) Proportion of subjects with new hospitalization or rehospitalization due to COVID-19 at 4 months and 6 months after randomization.
- w) Summarization of genotypic resistance analysis data.

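### SAP 10.3 counts any admission after the Day 43 visit, although the SAP's own endpoint (v) is limited to admissions due to COVID-19

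*SAP*

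**What the plan says.** **Limited to COVID-19.** The SAP endpoint list (3.2.3, item v) reads "Proportion of subjects with new hospitalization or rehospitalization due to COVID-19 at 4 months and 6 months after randomization". Protocol 10.6, which sets out what is asked at the Month 4 and Month 6 contacts, lists "Hospitalization or rehospitalization due to COVID-19 after Day 43". The Month 4 and Month 6 rows of the Schedules of Assessments (protocol Appendix A and SAP 16.1) carry the same restriction.

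**Silent on cause.** Protocol 8.3(d) reads "Proportion of patients with new hospitalization or rehospitalization after Day 43, at 4 months and 6 months after randomization". The synopsis says the same.

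**No cause criterion.** SAP 10.3 tabulates "subjects with any new hospitalization or rehospitalization during the entire long term follow-up" and counts a subject who has "at least one hospitalization with an admission date after the Day 43 follow-up visit". It names the Hospitalizations eCRF as its source, for admissions and dates of stay.

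SAP section 14 lists the changes from the planned analysis. It covers the Bristol stool types, the 0.5-day imputation and the absence of censoring for the last watery stool. It does not mention hospitalization.

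**The concern.** The endpoint and the rule that produces its number do not match. A programmer who follows SAP 10.3 applies a date test only, whereas a reader of endpoint (v) expects a cause test as well. The inconsistency lies inside the SAP (3.2.3 and 16.1 against 10.3), so it cannot be settled by saying that the SAP takes precedence over the protocol.

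At stake is what the reported proportion means. Protocol 5.2 gives a possible effect on long COVID as the reason for the 4- and 6-month follow-up, and hospitalization is one of only four items collected there. Admissions unrelated to COVID-19 would add events that do not bear on that question.

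**Working it through.** No figure in the plan depends on this definition, so there is nothing to reproduce. The check is a comparison of every statement of the endpoint, followed by what the counting rule returns under each possible state of the data.

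| Place | Role | Cause |
|---|---|---|
| Protocol synopsis, exploratory (u) | Endpoint | Not stated |
| Protocol 8.3(d) | Endpoint | Not stated |
| Protocol 10.6 | Data collected at Months 4 and 6 | COVID-19 |
| Protocol Appendix A | Schedule | COVID-19 |
| SAP 3.2.3(v) | Endpoint | COVID-19 |
| SAP 10.3 | Table content and counting rule | Any |
| SAP 13.2 | Description of the exploratory data | Tied to recurrence of COVID-19 symptoms |
| SAP 16.1 | Schedule | COVID-19 |
| SAP 14 | Declared changes | Endpoint not mentioned |

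**What the rule returns.** Among subjects who continued into long-term follow-up (the 10.3 denominator), let C be those with at least one COVID-19 admission after the Day 43 visit. Let U be those with at least one unrelated admission after that visit that was entered on the eCRF. Assume that all COVID-19 admissions are entered.

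- Numerator for endpoint (v): the number of subjects in C.
- Numerator under SAP 10.3: the number in C or U.
- Excess of 10.3 over (v): the number in U but not in C, that is, subjects whose only recorded admissions after Day 43 were unrelated.

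Three cases follow:

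1. No unrelated admission is entered: U is empty, the excess is zero, and 10.3 matches (v) under the wrong label.
2. All unrelated admissions are entered: 10.3 gives an all-cause proportion, which exceeds (v) by the excess above.
3. Some are entered: 10.3 lies between the two, depending on recording practice.

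**Can the documents exclude cases 2 and 3?** No.

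- The Hospitalizations eCRF also serves the Day 1 to Day 43 ICU and hospitalization endpoints (SAP 8.3.5 and 8.3.7). Those have no cause limit, so the form is used for admissions of any cause.
- Protocol 13.1.1 observes adverse events until the patient completes the study, which protocol 9.3 puts at about 6 months. Protocol 13.1.2 makes inpatient hospitalization a criterion for a serious event.
- Against that, SAP 9.1 ends adverse event observation at the Day 43 visit, and the schedules have no adverse event entry at Months 4 and 6.

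A site could therefore enter an unrelated admission in month 5, and another could leave it out, each following some part of the text. The SAP mentions admissions and dates of stay on this form, but not the reason for admission. Whether a cause filter could be applied is therefore also unknown.

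**The case against.** The strongest defence is that collection already does the filtering. SAP section 10 limits the exploratory analyses to data collected at the Month 4 and Month 6 visits. Protocol 10.6 asks there only about COVID-19 admissions, and SAP 13.2 ties the hospitalization data to symptom recurrence. On this reading, *any* in 10.3 means any of the admissions collected, and the result agrees with endpoint (v). That is case 1 above, and it may be what happens. It is not assured, because 10.3 takes its data from a form that is also used for admissions of any cause.

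A reader might go further than the documents allow in four ways:

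- **That the result is neither all-cause nor COVID-related, and so cannot be interpreted.** This does not follow. If only COVID-19 admissions are captured, the count is COVID-related without a filter; if all are captured, it is all-cause. Only partial capture gives a mixture, and nothing shows that this will occur.
- **That the protocol defines the endpoint as all-cause.** Protocol 8.3(d) does not state a cause. Read with 10.6 and Appendix A, it can be shorthand for the COVID-19 version. Only SAP 10.3 says any.
- **That capture of unrelated admissions will vary by site.** It may vary, since the instructions allow it. Neither document shows that it will.
- **That the arms would be affected differently.** SAP 4.2 keeps subjects, investigators and site staff blinded until Month 6 is complete, so the documents give no reason to expect recording to differ by arm.

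**Conclusion.** The point holds as a minor inconsistency. SAP 10.3, the only operative counting rule, lacks the cause restriction in the SAP's own endpoint (v), and SAP section 14 does not acknowledge the gap. As written, 10.3 can overcount endpoint (v) but cannot undercount it, provided that all COVID-19 admissions after Day 43 are entered.

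The overcount is the share of followed subjects whose only recorded admissions after Day 43 were unrelated to COVID-19. It is zero if none are recorded. The documents give no long-term admission rate and no split by cause, so any percentage would only restate an assumption, and none is given here.

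The reach is limited. SAP section 10 makes the exploratory analyses descriptive, with no inferential tests, and reports them in an addendum to the main study report. The primary analysis, alpha and power do not depend on this definition.

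**What to change.** 1. In SAP 10.3, restrict the event to an admission dated after the Day 43 visit and recorded as due to COVID-19, and drop *any* from the table description.
2. Confirm that the Hospitalizations eCRF records the reason for admission. The restriction in step 1 depends on it.
3. Align protocol 8.3(d) and the synopsis with protocol 10.6 and Appendix A by stating the cause.
4. Record the change in SAP section 14.
5. If all admissions after Day 43 are in fact captured, an all-cause proportion may be shown alongside, labelled as such.

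The cost is a clause in SAP 10.3, matching wording in two places in the protocol, and one entry in section 14. The work grows only if the eCRF has no reason for admission. That field would then have to be added, or the reason queried with sites, before the second database lock described in SAP 13.2.

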10.4. Summarization of genotypic resistance analysis data

Nasopharyngeal swabs and stool samples will be collected and stored for possible genotypic resistance analysis. The summary results will be provided when data become available.

11. Interim Safety Analysis

The interim safety data review for Part 1 and 2 of the study will be performed by the DMC (see [Section 12](#), below). Data to be reviewed includes subject disposition, demographics, medical history, concomitant medications, study drug Exposure and compliance, adverse Events, safety clinical laboratory and vital signs. The DMC will be unblinded to study data and will operate under a DMC charter. Blinded and unblinded PPD Biostatisticians will produce and provide tables, listings, and figures requested by the DMC.

Part 1 will enroll approximately 9 hospitalized subjects. After treatment is concluded for all 9 subjects, the DMC will review the safety data and determine if the study may proceed to Part 2 or if additional subjects are needed to assess tolerability of the study drug. If additional subjects are needed, approximately 9 more subjects will be enrolled in Part 1, and then the DMC will meet again after all subjects are treated to determine if the study may proceed to Part 2. Due to the relatively small number of subjects in Part 1, the decision for DMC review of Part 1 will be based on medical judgment of niclosamide tolerability compared to placebo and will not require specific statistics.

For Part 2, the planned interim safety data review will occur when 50 subjects have been randomized and completed the 2-week treatment period. The outcome from the DMC to be delivered to the sponsor will be: (1) continue as planned; (2) pause enrollment and undertake further evaluation of safety; or (3) recommend that the study be terminated due to safety concerns. No rigid statistical stopping rules will be used to make these decisions. While the DMC statistician may perform statistical analyses to examine adverse trends in safety, such as excess deaths and SAEs in the active arm, the decision to recommend a pause in enrollment or termination of the study will be reached by clinical consensus of the DMC.

No formal interim analysis for efficacy is planned to stop the study early for benefit or futility.

12. Data Monitoring Committee (DMC)

An independent Data Monitoring Committee (DMC) will be established to review the safety data throughout the study to ensure the safety of study subjects, the ethical continuation of the study, and provide recommendations regarding continuation or termination of the study or protocol modifications. The DMC will be headed by a DMC Chair and will consist of 2 clinicians and 1 biostatistician, who, collectively, have experience in the management of patients with infectious

diseases and in the conduct and monitoring of randomized clinical trials. The DMC will consist of experts independent from the Sponsor.

The roles, responsibilities and rules governing operation of the DMC are discussed in full in the DMC charter, which will be finalized prior to the administration of investigational product. The DMC charter will define the primary responsibilities of the DMC; guide its activities, its relationship with other study components, its membership, and the purpose and timings of its meetings. It will provide the procedures for ensuring confidentiality, formal communication, and outline of the content of reports that will be provided by the DMC.

13. Final Analyses and Unblinding

13.1. Day 43 Final Analysis

This analysis will be carried out for the main clinical study report (CSR) when the last subject has completed the Day 43 follow-up visit. The main CSR will contain all efficacy (primary and secondary) and safety data through Day 43 as specified per protocol for all randomized patients. An official database lock with PI sign off will be implemented prior to this final analysis at Day 43.

13.2. End of Study Final Analysis

This analysis will be provided in an addendum to the main CSR. It will include only exploratory data collected at Month 4 and Month 6 long-term follow-up visits. Specifically, the exploratory data contains subject survival status, recurrence of COVID-19 symptoms and associated hospitalization(s) and treatments/therapies. A second official database lock with PI sign off will be performed but only for exploratory data prior to this final analysis at end of long-term follow-up.

13.3. Unblinding

At the time of the final analysis at Day 43, the randomization will be unblinded to the central study team after the official database lock. However, the investigators, other site study staff, and subjects will remain blinded to their treatment allocation(s) for as long as they are participating in the study.

14. Changes in the Planned Analysis

Bristol Stool Scale Types 5-7 has been updated to 6-7 for the secondary endpoint in section 3.2.2, section 8.2.2, and section 8.2.3 to be consistent with Appendix B of the protocol. Furthermore, for both analyses if the day of the formed stool/last watery stool was the same as the first day of treatment, then the time to event was imputed as 0.5 days. In the time to last watery stool analysis, there was no censoring necessary.

15. References

Sato, T. (1989). On the variance estimator for the Mantel-Haenszel risk difference, *Biometrics* 45, 1323-1324. Letter to the editor.

16. Appendices

16.1. Schedule of Assessments

Visit ¹	Screening ²	Treatment				Follow-Up					
						Short-term				Long-term	
Timing (D=day, M=month)	D -3 to -1	D1	D4	D8	D15	D22	D29	D36	D43	M4	M6
Deviation vs randomization day			±1 day	±1 day	±2 days	±2 days	±2 days	±3 days	±3 days	±1 week	±1 week
Informed consent	X										
Eligibility (inclusion/exclusion criteria)	X	X									
Demography	X										
Medical history (or changes)	X	X	X	X	X	X	X	X	X		
Stool analysis	X										
Stool sample for SARS-CoV-2 RNA ³	X	X	X	X	X	X	X	X	X		
Diarrhea clinical assessment	X	X	X	X	X	X	X	X	X		
Nasopharyngeal swab for SARS-CoV-2 RNA ³	X	X	X	X	X	X	X	X	X		
Laboratory assessments ⁴ (L=local, C=central)	L	C		C	C			C		C	
Overall clinical assessment ⁵	X	X	X	X	X	X	X	X	X		
Randomization		X									

Dosing study drug		Daily TID, with last dose on D14 or 15										
Daily diary		Daily										
Adverse events	X	X	X	X	X	X	X	X	X			
Concomitant medications		X	X	X	X	X	X	X	X			
Survival status										X	X	
Persistence of COVID-19 symptoms										X	X	
Recurrence of COVID-19 symptoms										X	X	
(Re)Hospitalization due to COVID-19										X	X	

1. Patients may be hospitalized, inpatient in a research unit, or seen in an outpatient clinic or in a home care setting.
2. Screening may occur on the same day as randomization, if all procedures may be completed. If they occur on the same day, procedures scheduled for both visits are not required to be duplicated.
3. At screening, eligibility can be determined by local SARS-CoV-2 viral RNA analysis on a nasopharyngeal swab. Only one screening sample is required and can be determined by local requirements. Eligibility can be determined at a local laboratory at screening; however, a central laboratory may be used at screening if needed. On Days 1 to 43, the nasopharyngeal swab and stool sample will be collected and sent to the central lab.
4. Local laboratory testing at screening should include at least AST, ALT, and serum creatinine to determine eligibility. Central laboratory testing will include CBC, BUN, blood sugar, electrolytes (sodium, chloride, potassium, and bicarbonate [HCO3]), alkaline phosphatase, AST, ALT, LDH, total bilirubin, serum creatinine, C-reactive protein, and fecal calprotectin. When only central testing is required, any other laboratory assessment may be conducted at the local laboratory for the physician’s safety assessment according to the local practice and patient’s clinical needs.
5. Including: mortality; hospital admission and discharge; ICU admission and discharge; WHO severity score and duration, type of administration, vital signs, and quantity of supplemental oxygen treatment. Vital signs should be completed on Days 1-8, 10, and 12 for Part 1 patients, but only need to be recorded in the CRF when the full Overall Clinical Assessment is due at the study visits above.

* Initial medical history will collect date of initial symptom onset. If date is uncertain, verbatim response from patient will be collected.

